6.1.2 Baseline

Two types of Baseline will be defined: DB Baseline and Withdrawal Baseline. DB baseline is also referred as Baseline by default in this document.

6.1.2.1 DB Baseline for Assessment Based on Diary Data

See [Section 5.1.1](#) for definition of Baseline for eating diary based data.

6.1.2.2 DB Baseline for Other Data

Baseline is defined as the pre-dosing measure on Day 1. If it is missing, unless otherwise specified, it will be imputed by the latest non-missing measurement prior to Day 1.

6.1.2.3 Withdrawal Baseline for Assessment Based on Diary Data

Withdrawal Baseline is defined as the derived value at Week 12/EOT. See [Section 5.1.1](#)

6.1.2.4 Withdrawal Baseline for Other Data

See [Section 6.1.4.2](#) for the definition of Withdrawal Baseline. No imputation will be made if the withdrawal Baseline value is missing.

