6.4. Safety Endpoints

The safety endpoints are:

- The incidence of overall AEs, serious AEs (SAEs), and AEs (or SAEs) leading to discontinuations

- Clinical laboratory evaluations (serum chemistry, hematology, and urinalysis)
- Clinical evaluations (vital signs including orthostatic effects, and 12-lead ECGs)
- Frequency and severity of suicidal ideation and suicidal behavior as assessed by the C-SSRS
- Change and percent change from baseline in body weight at Weeks 1, 2, 3, 4, 6, 8, 10, and 12
- Change and percent change from baseline in BMI at Weeks 1, 2, 3, 4, 6, 8, 10, and 12
- Change from baseline in a fasting lipid panel (triglycerides, total cholesterol, high-density lipoprotein [HDL] cholesterol, and low-density lipoprotein [LDL] cholesterol) at Weeks 6 and 12
- Change from baseline in hemoglobin A1c level at Weeks 6 and 12
- Change from baseline in fasting glucose level at Weeks 6 and 12
- Change from baseline in insulin and high-sensitivity C-reactive protein (hs-CRP)
- Occurrence of symptoms of withdrawal from dasotraline measured by change from Week 12/EOT in:
 - CSSA total score at Weeks 13, 14, and 15
 - DESS total score at Weeks 13, 14, and 15
 - HAM-A total score at Weeks 13, 14, and 15
 - MADRS total score at Weeks 13, 14, and 15

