13.3. Clinical Assessments After Study Drug Discontinuation

Subjects who discontinue study medication before completion will be asked to return to the site and complete the EOT visit assessments ([Section 11.8.9](#)), as soon as possible following discontinuation of study drug, and complete the study medication withdrawal assessments and visits ([Section 11.8.10](#)).

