15.4.2. Safety Analyses

Safety data including AEs, laboratory values, ECG, vital signs, weight, C-SSRS, and other assessments will be analyzed by treatment group based on the DB Safety population (for data up to the end of treatment period) and Withdrawal safety population (for data collected during the withdrawal period), separately, as appropriate.

The data (including CSSA, DESS, MADRS, and HAM-A), which are used to assess physical dependence and withdrawal symptoms, will be analyzed by treatment for data collected in the withdrawal period based on the Withdrawal safety population.

Unless otherwise specified, for continuous data collected in the withdrawal period, the actual value and change from Week 12/EOT (last value during the treatment period) will be summarized by treatment and visit.

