6.1.4.2 Visit Window for Visits in Withdrawal Period

Visits within withdrawal period will be mapped per visit window defined in [Table 6.1](#) below for efficacy and safety data collected in withdrawal period except of binge eating diary data. For diary data, see [Section 5.1.1](#) for data derivation rule.

Table 6.1: Visit Window for Clinic Visits in Withdrawal Period for Non-Binge Eating Diary Data

Variables to be Applied	Time Interval (Day) ^a	Target Time Point (Day)	Analysis Visit (label on output)
CSSA, DESS	-5 to 1 ^(b)	0	Withdrawal Baseline
	2 – 10 ^(c)	7	Withdrawal Week 1
	11 – 17 ^(c)	14	Withdrawal Week 2
	18 – EOS ^(c)	21	Withdrawal Week 3
Other	-5 to 3	0	Withdrawal Baseline
	4 – 10	7	Withdrawal Week 1
	11 – 17	14	Withdrawal Week 2
	18 – EOS	21	Withdrawal Week 3
^a Relative to the day of the last dose of double-blind study medication ^b per phone contacts or clinic visits ^c for clinic visits only.			

If a subject has 2 or more visits in one analysis visit window, the visit closest to the targeted day will be used as the study visit for that analysis visit window. The other additional visit(s) will be denoted as an unscheduled visit and not included in the by-visit descriptive summary analyses. However, measurements from this/these other additional visit(s) may be included in the other safety analyses to assure all off-treatment measurements are included. If the 2 study visits occur with the same number of days from the target day within the same visit window, the later one will be considered as the study visit for that target day.

Non-clinic phone contact visits within withdrawal period will be mapped per visit window defined in [Table 6.2](#) below for CSSA and DESS specifically.

Table 6.2: Visit Window for Non-Clinic/Phone Contact Visits in Withdrawal Period

Variables to be Applied	Time Interval (Day) ^a	Target Time Point (Day)	Analysis Visit (label on output)
CSSA, DESS	1 – 2	1	Day 1-2
	3 – 4	3	Day 3-4
	5 – 6	5	Day 5-6
	7 – 8	7	Day 7-8
	9 – 10	9	Day 9-10
	11 – 12	11	Day 11-12
	13 – 14	13	Day 13-14
	15 – 16	15	Day 15-16
	17 – 18	17	Day 17-18
	19 – 20	19	Day 19-20
	21 – 22	21	Day 21-22
	23 – 24	23	Day 23-24
	25 – EOS ^(b)	25	≥ Day 25

^a Relative to the day of the last dose of open-label study medication
^b per phone contacts visits only.

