7.4.6 Assessments of Withdrawal Effects (CSSA, DESS, HAM-A, and MADRS)

CSSA total score, DESS total score, MADRS total score, and HAM-A total score will be summarized by presenting descriptive statistics (N, mean, median, and range) of observed values and change from withdrawal baseline by treatment and visit (ie, both clinic and non-clinic visits) for the withdrawal period.

A similar analysis will be performed by gender as well.

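### The SAP scores withdrawal change from a window ending Day 1 (CSSA, DESS) or Day 3 (HAM-A, MADRS) after the last dose, not from the protocol's Week 12/EOT value, so early discontinuers with a later EOT visit can lose their change scores

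*SAP*

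**What the plan says.** **Protocol.** Section 6.4 lists as a safety endpoint "Occurrence of symptoms of withdrawal from dasotraline measured by change from Week 12/EOT in" the CSSA, DESS, HAM-A and MADRS totals at Weeks 13, 14 and 15. Section 15.4.2 explains the reference for continuous withdrawal-period data: "the actual value and change from Week 12/EOT (last value during the treatment period) will be summarized by treatment and visit". It sets no limit in days from the last dose. Section 15.4.2.7 repeats Week 12/EOT as the reference for these four scales. On early stopping, Section 13.3 says "Subjects who discontinue study medication before completion will be asked to return to the site and complete the EOT visit assessments", and gives the timing only as "as soon as possible following discontinuation of study drug".

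**SAP.** Section 7.4.6 summarises "observed values and change from withdrawal baseline by treatment and visit". Table 6.1 (Section 6.1.4.2) accepts a Withdrawal Baseline from Day -5 to Day 1 relative to the last dose for CSSA and DESS, where the value may come "per phone contacts or clinic visits". For other non-diary data the window is Day -5 to Day 3. Section 6.1.2.4 adds: "No imputation will be made if the withdrawal Baseline value is missing". Diary data are treated differently. Under Section 6.1.2.3, "Withdrawal Baseline is defined as the derived value at Week 12/EOT". Section 6.1.1.1 ends the treatment period at the later of the last dose and the Week 12/EOT visit. Section 4 states that the SAP makes no change to the protocol's planned analyses.

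**The concern.** The two documents use different reference values for a listed safety endpoint, and the SAP does not say so. The difference matters for subjects who stop early. Their EOT visit takes place after the last dose, and it is the first time CSSA and DESS are given. Under the protocol's reference, any such subject with an EOT value and a later value has a change score. Under the SAP, the same subject has one only if the EOT visit, or a qualifying phone contact, falls close enough to the last dose.

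The loss is selective. It falls on discontinuers, including those who stopped for adverse events, and it can differ by arm. The change summaries would then lean towards completers. Because the windows end on different days, CSSA/DESS changes and HAM-A/MADRS changes can also rest on different sets of subjects. This is a drug studied under an abuse-potential monitoring plan, so the withdrawal summaries will be read closely.

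**Working it through.** **Step 1: who is at risk.** Protocol Section 15.1 takes 96 evaluable subjects per group and about 40% discontinuation. 96 / (1 - 0.40) = 160, which reproduces the planned group size. The implied number of early discontinuers is 160 - 96 = 64 per arm, or 192 of 480. The documents give no figure for missing withdrawal baselines.

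**Step 2: which visits can supply a baseline.** Day 0 is the last dose.

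- *CSSA and DESS.* Protocol Table 2 schedules neither before Week 12/EOT. Phone calls start on the second day after the last dose with a window of one day either side (Protocol 11.8.10), so a call can fall on Day 1, 2 or 3. Only a Day 1 call lies inside the SAP window. An EOT visit on Day 2 or later with no Day 1 call leaves no baseline.
- *HAM-A and MADRS.* Protocol Table 2 has no assessment between Baseline and Week 12/EOT. An EOT visit on Day 4 or later therefore normally leaves no baseline. The exception is someone who stops in the first few days, whose pre-treatment visit may lie inside the five-day look-back.
- *Vital signs, ECG, laboratory.* Vital signs are taken at every visit, and ECG and laboratory tests at some. A scheduled visit in the last five dosing days can supply the baseline.
- *Completers.* The visit is at Day 84, plus or minus one day, with study drug taken that morning, so both windows are normally met.

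**Step 3: what happens to a late EOT value.** Table 6.1 places it in Withdrawal Week 1 (from Day 2 for CSSA/DESS, from Day 4 otherwise). If a Week 13 visit is closer to Day 7, the EOT value becomes an unscheduled record and leaves the by-visit summary. For HAM-A and MADRS, SAP Table 4 maps the same visit to a treatment week, consistent with Section 6.1.1.1, so the SAP can place one visit in both periods. A Day 1 call can likewise be the baseline in Table 6.1 and the Day 1-2 outcome in Table 6.2.

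**Step 4: size, under stated assumptions.** The delay from last dose to EOT visit is not given. Assume that all 64 discontinuers per arm return and that the delay in whole days is geometric with mean g. With r = g / (1 + g):

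- CSSA/DESS baseline missing = P(delay of 2 days or more) x (1 - q) = r² x (1 - q), where q is the share with a Day 1 call, taken as 0 or 1/3;
- HAM-A/MADRS baseline missing = P(delay of 4 days or more) = r⁴.

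| Mean delay g | r | CSSA/DESS, q = 1/3 | CSSA/DESS, q = 0 | HAM-A/MADRS |
|---|---|---|---|---|
| 1 day | 0.500 | 17% (11 of 64) | 25% (16) | 6% (4) |
| 3 days | 0.750 | 38% (24) | 56% (36) | 32% (20) |
| 7 days | 0.875 | 51% (33) | 77% (49) | 59% (38) |

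Under the protocol's reference, the window removes none of these subjects.

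**Step 5: drug remaining at a late visit.** With the half-life of 47.1 to 77.0 h (Protocol 4.2), the fraction left is 0.5^(hours / half-life). That is 49% to 65% at 48 h and 35% to 52% at 72 h.

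**The case against.** The strongest objection is that a window close to the last dose is the better reference. Step 5 shows that a late EOT score may already contain withdrawal symptoms, so using it as the reference would shrink the change and could hide a signal. The protocol's glossary (Table 4) supports this reading in part: it defines End of Treatment as the day of the last dose and the treatment period as the time drug is given. On that definition, a score taken days later is not a treatment-period value. This stands as a reason to keep a windowed summary and it shows that the protocol is ambiguous. It does not explain why the SAP's own treatment period runs to the EOT visit, why CSSA and DESS stop at Day 1 while HAM-A and MADRS run to Day 3, or why the departure is not declared.

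Stronger readings are tempting, and the documents do not support them:

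- A reader might infer that every EOT visit on Day 2 or later loses CSSA and DESS. A Day 1 call can supply the baseline.
- A reader might infer that from Day 4 no vital signs, ECG or laboratory baseline exists. Visits in the last five dosing days can serve.
- A reader might infer that late EOT scores are generally reported as Week 1 outcomes. The closest-to-Day-7 rule displaces an EOT visit on Days 2 to 5 whenever the Week 13 visit, due 6 to 8 days after the last dose, takes place on time.
- A reader might infer that many discontinuers are lost. That depends entirely on delays the documents do not state. Subjects who never return have no EOT value under either definition.

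The impact is also bounded. The stated withdrawal objective concerns stopping after 12 weeks of continuous treatment, and completers are largely unaffected. The summaries are descriptive and observed scores are still shown. DESS counts only new or worsened symptoms, so its observed total is informative without a baseline.

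**Conclusion.** The inconsistency is real and undeclared. For the four withdrawal scales, the SAP uses a reference that can exclude early discontinuers whom the protocol's reference would keep. The mechanism follows directly from the visit schedule and Table 6.1. Its size does not. Roughly 17% to 77% of returning discontinuers (about 11 to 49 of 64 per arm) would lack a CSSA/DESS baseline, and 6% to 59% (about 4 to 38) a HAM-A/MADRS baseline. These figures hold only under 40% discontinuation, full return for EOT, a geometric delay with mean 1 to 7 days, and none or one third having a Day 1 call. The range runs from a minority to a majority, so the plan cannot be said to lose most or even many of them.

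Power, type I error and the efficacy conclusions are untouched. What is at stake is whether the change summaries for a listed safety endpoint represent those who stopped early. That is worth settling before database lock, because the correction is cheap.

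**What to change.** 1. Reconcile SAP Table 6.1 and Section 6.1.2.4 with the protocol: summarise change from the Week 12/EOT value for every subject who has one, without a day limit.
2. Keep the near-last-dose window as a companion summary, with one upper limit for all four scales. The SAP already accepts Day 3 for HAM-A and MADRS.
3. State that an EOT value serving as the reference cannot also be a withdrawal-period outcome. If it is the only value in the Week 1 window, the Week 1 change is missing. Apply the same rule to a Day 1 call used as baseline.
4. List the windowed baseline as a departure in SAP Section 4, with its rationale.
5. Report by arm the number of subjects without a windowed baseline.

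The cost is SAP wording, programming and one further set of descriptive tables; no new data are needed. The downside is that some reference values will have been taken days after the last dose and may shrink the change scores, which is why both versions should be shown side by side.

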6.1.3 Endpoint

6.1.3.1 Week 12 Endpoint

Week 12 Endpoint is defined as the last post-baseline non-missing assessment in the treatment period. Hereafter, for the sake of simplicity, Week 12 Endpoint will be referred as Endpoint by default.

6.1.3.2 Withdrawal Endpoint

Withdrawal Endpoint is defined as the last non-missing post-withdrawal baseline assessment in the withdrawal period (regardless of clinic or non-clinic visits).

6.1.4 Visit Windows

6.1.4.1 Early Termination (ET) Visit in Double-Blind Treatment Period

All data are organized and analyzed according to the scheduled times as outlined in the protocol and by the visit denoted on the electronic case report form (eCRF), except for early termination (ET) visits during the treatment period. If a subject terminates early during the DB treatment period, the early termination visit (ie, EOT visit) will be re-mapped using the study day of the visit in [Table 4](#), which applies on both efficacy and safety data per a specific rule associated with that measurements except of the variables derived from binge eating diary. [Table 5](#) describes the remapping rules applied to diary data at ET visits.

Table 4: Visit Window for Early Termination Visit in Treatment Period for Non-Binge Eating Diary Data

Last Scheduled Visit	Time Interval (Day) ^a	Analysis Visit (label on output)
Baseline *	≥ DLSV+1	Week 1
Week 1	≥ DLSV+1	Week 2
Week 2	≥ DLSV+1	Week 3
Week 3	≥ DLSV+1	Week 4
Week 4	≥ DLSV+1	Week 6
Week 6	≥ DLSV+1	Week 8
Week 8	≥ DLSV+1	Week 10
Week 10	DLSV+1 – EOT	Week 12

^a Relative to the day of the first dose of double-blind study medication DLSV=study day of last scheduled visit relative to the first dose of study medication *: for the study day of the ET visit > Day1 Note: Applicable scope of Table 4: vital sign, weight and BMI, C-SSRS, HAM-A, MADRS, EDE-QM, lab, ECG, PK, neurological exam, and breath alcohol test.
 
BE-CGI-S and Y-BOCS-BE: if the last scheduled visit is Baseline or Week 1, the ET visit will be mapped to Week 2; if the last scheduled visit is Week 2 or Week 3, the ET visit will be mapped to Week 4; if the last scheduled visit is Week 4 or after, the ET visit will be mapped same as Table 4 SDS: if the last scheduled visit is prior to Week 6, the ET visit will be mapped to Week 6; if the last scheduled visit is at/after Week 6, the ET visit will be mapped to Week 12.
		

Only protocol planned visits for each measurement (ie, Baseline, Weeks 1, 2, 3, 4, 6, 8, 10, and 12 as appropriate) are included in the by-visit analyses. That is to say, the unscheduled visits will not be included in the by-visit summary; however, measurements from this/these additional visit(s) will be included in the safety analyses (eg, markedly abnormal value in treatment period, the worst case analysis etc.) to assure all on-treatment measurements are included.

Table 5: Visit Window for Early Termination Visit in Treatment Period for Binge Eating Diary Data

Last Scheduled Visit	Time Interval (Day) ^a	Analysis Visit (label on output)
Baseline *	DLSV – DLSV+30	Week 1
Week 1	DLSV – DLSV+30	Week 2
Week 2	DLSV – DLSV+30	Week 3
Week 3	DLSV – DLSV+30	Week 4
Week 4	DLSV – DLSV+40	Week 6

321

Week 6	DLSV – DLSV+40	Week 8
Week 8	DLSV – DLSV+40	Week 10
Week 10	DLSV – DLSV+40	Week 12
^a Relative to the day of the first dose of double-blind study medication DLSV=study day of last scheduled visit relative to the first dose of study medication *: for the study day of the ET visit > Day 1		

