5.1. Efficacy Variables

5.1.1. Variables Derived Per Binge Eating Diary

All binge episodes will be captured daily by the subject in a binge eating diary using paper format to record the date, duration (total hours of binging), type of binge episode (meal or non-meal), amount and type of food, and number of binges. The number of binge days per week and the number of binge episodes per week at each assessment timepoint will be derived based on clinician review of the binge eating diary collected in the time intervals as follow:

- Baseline: binge eating diary completed for 14 consecutive days immediately prior to the Baseline visit;
- Weeks 1, 2, 3, and 4 (ie, Visits 3, 4, 5, and 6): binge eating diary collected at each visit, which will span from the previous visit to the current visit and therefore cover Weeks 1, 2, 3, and 4, respectively; Particularly, Week 1 visit period will span from Day 1 (ie, 1st dose day) to one day before Week 1 visit date (inclusive).
- Weeks 6, 8, 10 and 12 (ie, Visits 7, 8, 9, and 10): binge eating diary collected at each visit, which will span from the previous visit to the current visit and therefore cover Weeks 5/6, 7/8, 9/10, and 11/12, respectively.
- Withdrawal Weeks 1, 2, 3 (ie, Week 13, 14, and 15): binge eating diary collected at each withdrawal visit, which will span from the previous visit to the current visit and therefore cover Visits 11, 12, and 13, respectively.

Specifically, the diary information collected on the post-DB baseline visits will be counted into the corresponding week span; for an example, diary collected on Week 1 visit data will be counted into the diary data at Week 1; diary collected on Week 2 visit data will be counted into the diary data at Week 2; and so on.

Diary records reviewed at early termination visit will be mapped into scheduled visit. Mapping rule of early terminated visit for binge eating diary based on study day is provided in [Section 6.1.4.1](#).

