For very rare situations, a subject might miss a scheduled visit and come back at the next scheduled visit. For such a case, diary records are expected to be collected continuously without interruption. The collected diary will be reviewed on the next scheduled visit. During the double-blind treatment period, if a diary contains binge eating diary records for a missed visit, the diary records will be split into two parts by using the target day of the missed visit (see Table 2 in study protocol) as a data cut: part 1 starts from the previous scheduled visit date (inclusive)

321

to the target day of the missed visit (exclusive), and part 2 starts from the target day of the missed visit (inclusive) to the current visit (exclusive). Part 1 and Part 2 data will be used to derive binge diary related variables for previous scheduled visit and the missed visit, respectively.

5.1.1.1. Number of Binge Days, Number of Binge Episodes, and Number of Assessed Days During a Visit Period

Number of assessed days at baseline will be 14 days. The number of binge eating days per week at baseline is calculated as the number of binge eating days in the 14 days immediately prior to the Baseline visit multiplied by 7 and divided by the number of days in the Baseline period. No missing diary entry is expected. In case there is a missing diary, the non-missing diary days in 14 days immediately before randomization will be used to derive these variables.

For each post-baseline assessment visit defined in [Section 5.1.1](#),

- Number of assessed days within the visit period is defined as the difference in study day between the current visit and the previous visit (ie, study day of current visit – study day of previous visit). If missing diary entries exist during the assessed period for a subject, the number of assessed days will be derived based on the days with non-missing diaries.
- Number of binge days is counted as the binge days that occur between the previous visit date (inclusive) and a day before the current visit date (inclusive).
- Number of binge episodes is counted in a similar way. If missing diary entries exist during the assessed period for a subject, number of binge days and number of binge episodes will be derived based on the days with non-missing diaries.

5.1.1.2. Number of Binge Days per Week and Number of Binge Episodes per Week for a Visit Period

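### Early-termination visits are labelled from the last scheduled visit, not by study day, so up to 30 or 40 diary days can become one visit value and later diary returns have no visit

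*SAP*

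**What the plan says.** Two places in the SAP describe the mapping as driven by study day. Section 5.1.1 points to section 6.1.4.1 for the "Mapping rule of early terminated visit for binge eating diary based on study day", and 6.1.4.1 says the ET visit "will be re-mapped using the study day of the visit".

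The tables work differently. Each row starts from the last scheduled visit and gives one label. The anchor is defined as "DLSV=study day of last scheduled visit relative to the first dose of study medication".

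- **Table 5 (diary).** The ET visit may fall up to DLSV+30 (last visit Baseline to Week 3) or DLSV+40 (Week 4 to Week 10). All of it takes the label of the next visit.
- **Table 4 (other data).** Rows for last visits Baseline to Week 8 start at DLSV+1 and have no end. The Week 10 row ends at EOT, which for these subjects is the ET visit itself.
- **Scale-specific notes.** For BE-CGI-S and Y-BOCS-BE, "if the last scheduled visit is Baseline or Week 1, the ET visit will be mapped to Week 2", and "if the last scheduled visit is Week 4 or after, the ET visit will be mapped same as Table 4". For SDS, "if the last scheduled visit is at/after Week 6, the ET visit will be mapped to Week 12".

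Section 5.1.1 has a separate rule for a subject who misses a visit and comes back at the next one: "the diary records will be split into two parts by using the target day of the missed visit". It gives the first part to the previous scheduled visit and the second part to the missed visit.

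**The concern.** The label does not depend on when the subject came back. Study day only decides whether the ET visit falls inside a wide interval. Scheduled visits are 7 days apart to Week 4 and 14 days apart after that, so limits of 30 and 40 days matter only when at least one visit has been passed. In that case diary days from several scheduled intervals are averaged into the earliest of them, and the intervals they belong to are left missing.

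These values enter the primary MMRM, where visit is categorical, and the LOCF and dropout-profile analyses. The BE-CGI-S and Y-BOCS-BE models take ratings labelled in the same way. After a last visit at Week 10, the value affected is the Week 12 primary value itself.

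**Working it through.** **Inputs.** Target days 7, 14, 21, 28, 42, 56, 70 and 84 (protocol Table 2). A diary period runs from the previous visit day up to the day before the current visit, so assessed days = current visit day minus previous visit day (SAP 5.1.1.1). Upper limits DLSV+30 and DLSV+40 (Table 5). Visits are taken as on target. Last scheduled visit is read as the last one the subject attended. The SAP does not define it, but the 30- and 40-day limits would have no use otherwise.

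**Longest spans Table 5 allows**

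| Last visit | ET day | Diary days used | Label | Days by scheduled interval | Share in labelled interval |
|---|---|---|---|---|---|
| Week 2 (Day 14) | 44 | 14-43 = 30 | Week 3 | 7 / 7 / 14 / 2 in Weeks 3 / 4 / 6 / 8 | 7/30 = 23% |
| Week 4 (Day 28) | 68 | 28-67 = 40 | Week 6 | 14 / 14 / 12 in Weeks 6 / 8 / 10 | 14/40 = 35% |
| Week 10 (Day 70) | 110 | 70-109 = 40 | Week 12 | 14 in Week 12, 26 after Day 83 | 14/40 = 35% |

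In the last row, 26/40 = 65% of the Week 12 value is recorded after Day 83. Post-period days already outnumber Week 12 days for an ET visit on Day 99 (Days 70-98: 14 against 15).

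**First ET day with no diary row** (DLSV+31 or DLSV+41): Days 30, 38, 45, 52, 69, 83, 97 and 111 for last visits Baseline and Weeks 1, 2, 3, 4, 6, 8 and 10. After Week 4, an ET visit on Day 69 leaves 69 - 28 = 41 diary days unmapped. All 41 lie inside scheduled intervals (14 in Week 6, 14 in Week 8, 13 in Week 10).

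**Ratings.** A BE-CGI-S or Y-BOCS-BE rating at an ET visit on Day 84 is labelled:
- after last visit Week 1: Week 2, 84 - 14 = 70 days too early;
- after Week 2: Week 4, 84 - 28 = 56 days;
- after Week 4: Week 6, 84 - 42 = 42 days.

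The BE-CGI-S covers only the past 7 days (protocol 11.3.5).

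**Drug status.** One 10-capsule pack is dispensed per visit through Visit 5 (Week 3), and two packs after that (SAP 3.2). The longest spans exceed one dispensing by 30 - 10 = 20 or 40 - 20 = 20 days, assuming no carried-over capsules. SAP 6.1.1.1 extends the treatment period to the EOT visit, while 6.1.1.2 starts the withdrawal period right after the last dose. The same diary days can therefore fall in both.

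**Size at Week 12.** Assume 1.2 binge days/week in Weeks 11/12 and 3.2 afterwards (neither figure is in the documents). The value becomes (14 × 1.2 + 26 × 3.2)/40 = 100/40 = 2.5 instead of 1.2. With 96 subjects per arm, the number the sample size rests on, one such subject moves the arm mean by 1.3/96 = 0.014, or about 0.01. The planned differences are 0.9 and 0.8.

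**Frequency.** Not stated. The planned 40% discontinuation gives 0.40 × 480 = 192 subjects with a possible ET visit. If 5% to 20% of them return after missing a visit (assumed), that is 10 to 38 subjects over all rows. Only those last seen at Week 10 reach the Week 12 value directly.

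**The case against.** The strongest reply is that this will be rare. The protocol asks for the EOT visit promptly after drug is stopped (sections 7.1 and 13.3), and the extreme cases need gaps of 30 to 41 days. An ET visit on Day 110 is later than the Week 15 target, Day 105. Similar late returns across arms would partly cancel. The 4-week cessation endpoint uses the last 28 diary days directly, so Table 5 does not affect it. All of this stands, and it limits the size. It does not make the tables agree with the text, and Table 5 itself provides for the long spans.

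Four stronger readings are tempting, and the documents do not support them:

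- **All late returns are lost.** This is true of the diary only. Table 4 gives every late rating a label.
- **The missed-visit rule is contradicted outright.** It is written for a return at the next scheduled visit, and section 5.1.1 sends ET diaries to 6.1.4.1. The SAP does not say whether the split also applies to them. If it does, some long spans would be divided, but to different labels: the general rule gives a segment to the visit that ends it, whereas the split gives the first part to the previous visit.
- **Dropout categories in 7.2.3.2.6 come into conflict.** A subject last seen at Week 2 with ET on Day 44 has a last value labelled Week 3. The date-based example gives a different category only if Day 44 is the discontinuation date. If drug ran out around Day 24 (14 + 10), both give Weeks 3/4.
- **Late values are off drug.** The supply arithmetic makes this possible, not established.

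**Conclusion.** The point holds as a contradiction between the SAP's description and its tables, in the derivation of the primary variable. Followed literally, Table 5 can produce a Week 12 primary value made mostly of diary recorded after the 12-week period. It can also average several scheduled intervals into the earliest one, or drop a diary whose days all lie inside scheduled intervals. For ratings, the fault is an open-ended label, not loss of data.

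A reader might infer that the primary result is at serious risk. The documents do not support that. The frequency is unknown, the EOT visit is meant to be prompt, and the illustrated effect is about 0.01 binge days/week per affected subject per 96 in an arm. That figure rests on the assumed rates of 1.2 and 3.2 and on the longest permitted span after Week 10. The day counts assume on-target visits and the last-attended reading of the anchor. The point is worth fixing before database lock because it is cheap to do and because two programmers could build different primary datasets from the same diary.

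**What to change.** **Table 5 (diary).** Cut an ET diary at the protocol target days and give each segment the visit whose interval contains it. End the Week 12 span at the Day 84 (+1) window. Remove the DLSV+30/+40 cut-off so that days inside a scheduled interval are kept. Exclude days after the Week 12 window from the Week 12 value, and assign them to the withdrawal period only if they follow the last dose, as 6.1.1.2 requires.

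**Section 5.1.1.** Align the labels in the missed-visit split with this, so that one rule covers missed and ET visits.

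**Table 4 (ratings and other data).** Reconcile the study-day wording with the table, and add an upper limit so that a rating made beyond the labelled visit's interval is not analysed as that visit. Whether such a rating then counts at a later visit should be stated as an estimand choice, not left to the mapping. For example, moving a Day 84 BE-CGI-S after a last visit at Week 4 to Week 12 could put an off-drug value at the main time point, since the 20 capsules dispensed would last to about Day 48.

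**Cost.** SAP wording and derivation code before database lock, with no new data. The downside is a few short segments at the ends of ET diaries. The Day 44 example would give a Week 8 value based on two days.
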